5.2 Secondary study parameter(s)

Data obtained during this study will be checked for distribution. Normal data will be analysed using ANOVA analysis or student t-test. Non-parametric data will be analysed with Mann Whitney U-test or Kruskall wallis. Categorical data will be compared using chisquare or Fisher's exact test. A logistic regression model will be performed to assess independent association between number of transfusions and outcome (mortality and ICU length of stay). Results of the logistic regression will be reported as adjusted odds ratio (OR) with 95% confidence intervals.

If a sufficient number of patients can be included, propensity score matching for a liberal and a restrictive transfusion regime will be performed for each type of product. The criteria for a liberal an restrictive transfusion regime for red blood cells, platelets and plasma will be determined during the study. A p-value <0.05 will be considered to be significant.

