2. STUDY DESIGN

This study is a prospective, descriptive study and only includes objective data collected as part of routine care. No intervention takes place. ICUs in different world regions will be asked to participate in this study. Each centre can choose a week to participate from several pre-specified weeks. All newly admitted patients on the ICU in that specific week will be included and followed until discharge and/or 28 days (see Figure 1 for study flow).

A transfusion event is defined as the administration of a blood derived product or coagulation factor with as aim to treat or prevent anaemia, bleeding and/or coagulopathy. This includes administration of red cell concentrates, platelet concentrates, plasma and coagulation factors including fibrinogen concentrate, cryoprecipitate and prothrombin complex. For each transfusion event data will be collected prospectively using a questionnaire on prescription behaviour. Also transfusions administered on the operating theatre while admitted to the ICU will be included for analysis.

The daily questionnaire contains clinical an laboratory data. These data include nadir haemoglobin levels, platelet count and INR or PT. This data will be necessary to compare data between patients who did receive a transfusion to patients who did not receive transfusions. Furthermore, information about 24h fluid balance and anticoagulants administration will be collected. Finally after 28 days patient outcome data: length of ICU stay and 28-day mortality will be collected.

STUDY POPULATION

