2.4 Sample size calculation

It is planned to recruit 10 000 patients. The CRIT study and European data reported RBC transfusion rate of 30 to 40% for patients during their stay on the ICU. Furthermore transfusion rates for platelet concentrates and plasma of 12% and 9% have been reported^{17,22}. However, in this study we will include all transfusion events during a prespecified week and day. Depending on the study design, it is estimated that approximately 10-20% of all patients will receive at least one blood product, resulting in a total of approximately 1000-2000 transfusion events. As for the primary outcome merely descriptive statistics will be used, this will be a sufficient number of transfusion events. This is in accordance with data available from the most recent study investigating transfusion practices worldwide, in which 10.069 patients were included¹⁹.

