3.1.2 Secondary study parameters/endpoints

Secondary parameters will be:

- Mortality and length of stay in the ICU.
- Differences of transfusion regimes between world regions
- Differences of transfusion practices between different patient subgroups

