3.2 Data collection

All newly admitted patients at the ICU older than 18 years will be included for seven consecutive days. At the start, baseline characteristics will be scored prospectively. Also, patients will be scored daily using daily questionnaires until discharge with a maximum of 28 days. At the day 28, patient outcomes are scored irrespective whether they were discharged. Furthermore, for each transfusion event or administration of coagulations factors a questionnaire will be filled in. See Figure 1 for the workflow.

Figure 1. Workflow InPUT study

The following data will be collected:

Baseline characteristics:

- Demographics
- SOFA score at inclusion
- Type of admission
- Presence or absence and the type of shock on the study day
- Heart rate, systolic and diastolic blood pressure
- Ventilator settings
- Renal replacement therapy during that day

Questionnaire per transfusion event:

- General
 - \circ Active bleeding
 - Bleeding control
 - Red cell transfusion
 - Haemoglobin(Hb)/haematocrit (Ht) level
 - Hb threshold for this patient
 - Presence of physiological trigger, and which trigger has been used.
 - Transfusion relevant comorbidity

- Number of units transfused
- Origin of transfusion product (e.g. allogeneic, autologous, cell salvaged blood)
- Platelet transfusion
 - Platelet count prior to transfusion
 - Platelet count threshold for transfusion for this patient
 - Type of Platelet concentrate
 - Anticoagulant usage the past 72 hours
 - Usage of point of care to assess blood coagulation: ROTEM or multiplate
 - Number of units transfused
 - Upcoming procedures
- Plasma
 - INR prior to transfusion
 - $_{\odot}$ Anticoagulant usage the past 72 hours
 - Usage of point of care to assess blood coagulation
 - Amount of plasma transfused
 - Upcoming procedures
- Prothrombin complex concentrate (i.e. Cofact ®).
 - o INR or PT
 - Dosage of prothrombin complex concentrate
 - Usage of point of care to assess blood coagulation
 - Upcoming procedures
- Massive transfusion protocol:
 - Lowest haemoglobin level
 - Lowest platelet count
 - o INR
 - Usage of point of care to assess blood coagulation
 - Number of Red blood cell units transfused
 - Number of platelet concentrate units transfused
 - Amount of plasma transfused
 - Tranexamic acid, fibrinogen, rFactor VIIa, Cryoprecipitate, factor XIII, apropitin, novoseven (=eptacog alfa)
 - Bleeding control

Daily questionnaire

- Estimated blood loss
- Total number of transfused RBCs

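### Section 5.2 names only unadjusted tests for comparing groups, so a difference in case mix between world regions can be reported as a difference in transfusion practice

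*Protocol*

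**What the plan says.** The Summary sets out to compare transfusion practice between and within three world regions (Europe, America and Asia). Section 3.1.2 carries this into the secondary parameters: "Differences of transfusion regimes between world regions".

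Section 5.2 gives the methods for secondary parameters by type of data. For normally distributed data, "Normal data will be analysed using ANOVA analysis or student t-test". Non-normal data go to Mann-Whitney or Kruskal-Wallis. For the rest, "Categorical data will be compared using chisquare or Fisher's exact test". Significance is set at p<0.05. None of these tests carries covariates.

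Section 5.2 has two further analyses. One is a logistic model relating number of transfusions to mortality and ICU length of stay, reported as adjusted odds ratios. The other is propensity score matching of liberal and restrictive regimes for each product, if numbers allow. Neither has region as the compared factor.

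On recruitment, section 2 says "ICUs in different world regions will be asked to participate in this study". Each centre picks its week from a set list, and every newly admitted adult enters. No balancing of case mix or ICU type between regions is described. Section 3.2 lists the baseline items: "SOFA score at inclusion", demographics, type of admission, and presence and type of shock.

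**The concern.** Transfusion in an ICU depends both on how clinicians decide and on whom they admit. The introduction stresses how heterogeneous ICU patients are, and section 2.5 lists groups the sponsor wants to examine separately, such as cardiothoracic surgery, septic shock, haematology and ECMO. If the participating ICUs of one region admit more patients of a high-transfusion kind, that region's crude figures rise even where the same patient would be treated identically everywhere.

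A crude test cannot separate the two causes. With thousands of patients per region, a modest case-mix difference may be enough to reach p<0.05. The study's statement on regional practice, which is meant to inform guidelines, would then rest partly on the mix of ICUs that took part.

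This is confounding by case mix. Clustering of patients within ICUs is a separate matter and is not in the figures below.

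**Working it through.** **The plan's own figure.** Section 2.4 states "It is planned to recruit 10 000 patients" and expects that "approximately 10-20% of all patients will receive at least one blood product", "resulting in a total of approximately 1000-2000 transfusion events". 10,000 × 0.10 = 1,000 and 10,000 × 0.20 = 2,000, so the figure reproduces. No effect size or power is given for regions.

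**Inputs from the protocol.** Total 10,000; three regions; 10-20% of patients transfused; significance level 0.05.

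**Assumptions.** Equal regions (10,000 / 3 ≈ 3,333 each). Two admission strata, low-use and high-use, with the same transfusion rates in every region, so practice is identical. Only the high-use share s differs.

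**Crude rate in a region** = s × (high rate) + (1 − s) × (low rate). With rates of 10% and 30%:

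- s = 20%: 0.2 × 0.30 + 0.8 × 0.10 = 14%
- s = 25%: 0.25 × 0.30 + 0.75 × 0.10 = 15%
- s = 30%: 0.3 × 0.30 + 0.7 × 0.10 = 16%
- s = 40%: 0.4 × 0.30 + 0.6 × 0.10 = 18%

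All lie within the protocol's 10-20%.

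**How often each test finds a regional difference** (4,000 simulated studies per row). The crude test is the three-group chi-square. The stratified test is the generalised Cochran-Mantel-Haenszel test across the two strata.

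| Strata rates | High-use shares | Crude rates | Crude test | Stratified test |
|---|---|---|---|---|
| 10/30% | 25/25/25% | 15/15/15% | 4.6% | 5.4% |
| 10/20% | 20/25/30% | 12/12.5/13% | 17.2% | 5.0% |
| 10/30% | 20/25/30% | 14/15/16% | 50.5% | 5.3% |
| 10/30% | 20/30/40% | 14/16/18% | 98.5% | 5.2% |

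With regions of 7,000/1,500/1,500, the three unequal rows give 16.0%, 46.4% and 96.9% for the crude test. Over all unequal-mix scenarios tried (strata 10/20%, 10/30%, 10/40% and 5/35%; shares up to 10/30/50%), the crude test rejected in 16-100% and the stratified test in 4.6-5.5%.

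**Check by formula.** The chi-square has 2 degrees of freedom and non-centrality λ = n Σ(pᵢ − p̄)² / [p̄(1 − p̄)].

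- 14/15/16%: 3,333 × 0.0002 / (0.15 × 0.85) = 5.23, rejection about 52%
- 14/16/18%: 3,333 × 0.0008 / (0.16 × 0.84) = 19.84, about 98.5%
- 12/12.5/13%: 3,333 × 0.00005 / (0.125 × 0.875) = 1.52, about 18%

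These agree with the simulation. In the second case the outer regions (14% and 18%) show an odds ratio of (0.18/0.82)/(0.14/0.86) = 1.35 with no difference in practice.

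**Pre-transfusion haemoglobin.** Assume strata differ in mean by 0.5 or 1.0 g/dl, the SD is 1.2, and the stratum share among transfused patients differs by 20 points between two regions. The spurious mean difference is 0.2 × 0.5 = 0.1 or 0.2 × 1.0 = 0.2 g/dl. With 1,000/3 ≈ 333 to 2,000/3 ≈ 667 transfused patients per region, a two-sample test finds it in 19-33% or 58-86% of studies. The distortion is smaller here but present.

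**The case against.** **Section 5.2 is a generic list.** It assigns no test to the region comparison and does not rule out adjustment, and covariates are often left to a statistical analysis plan, which may exist. A reader might infer that the sponsor has decided regional conclusions will rest on crude tests alone; the text does not go that far. What remains is that the protocol names unadjusted tests for comparing groups and attaches adjustment only to other questions. That is a stated method, not just a gap.

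**Transfusion is related to trigger values.** The main parameter sets units against pre-transfusion haemoglobin, platelets, INR or PT and fibrinogen (section 3.1.1), and patient-level haemoglobin and platelet thresholds are recorded. Such measures come closer to practice than a transfusion rate. This limits the distortion, but trigger values can themselves vary with case mix.

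**Subgroup analyses report by case mix.** Section 2.5 plans them for ten groups, but only if numbers suffice, and does not say that regions will be compared within them.

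**The study is descriptive.** Section 5.1 restricts only the primary endpoint to description. A crude regional description is legitimate; the fault lies in reading a tested crude difference as practice.

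**Stronger readings.** A reader might infer that the ICUs are self-selected, that some region will certainly look more liberal, or that the patient-subgroup comparisons share the fault. The protocol says only that ICUs are invited and choose a week. It gives no regional case mix, so the direction and size are unknown. For subgroups, admission type or shock may define the group, and adjusting for them could remove the contrast of interest.

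**Conclusion.** The point stands for comparisons between regions and between centres. As written, section 5.2 lets a case-mix difference be declared a regional difference in practice, and none of its adjusted analyses prevents this.

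The size is conditional. With equal case mix the crude test holds its 5% level. With the assumed imbalances it is wrong in anything from about one study in six to nearly all. Stratum rates, shares and region sizes are assumptions, and the transfusion rate is the outcome most exposed. The documents do not show that the imbalance will occur, only that nothing described prevents it. Because this is a secondary parameter and the data for a remedy are already collected, it should be corrected but does not threaten the primary description.

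**What to change.** Add to section 5.2, for example:

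*Differences between world regions and between centres in transfusion (any transfusion, units given, pre-transfusion value) will be estimated by regression adjusted for type of admission, SOFA score at inclusion, shock and age, or standardised to the pooled case mix. Crude figures will be shown alongside. Conclusions on regional practice will be based on the adjusted estimates.*

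Limit this to regions and centres. Leave the patient-subgroup contrasts out of this rule.

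Cost: a change of wording and a little more analysis. No new data are needed, but the result depends on how completely the baseline items are recorded. Adjustment removes only the case mix that these items capture.

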	company, academic hospital, scientific organisation or investigator. A			
	party that provides funding for a study but does not commission it is not			
	regarded as the sponsor, but referred to as a subsidising party.			
Wbp	Personal Data Protection Act (in Dutch: Wet Bescherming			
	Persoonsgevens)			
WMO	Medical Research Involving Human Subjects Act (in Dutch: Wet Medisch- wetenschappelijk Onderzoek met Mensen			

SUMMARY

Rationale: Since a transfusion guideline specific for intensive care patients is currently lacking, we expect a large heterogeneity in transfusion practice worldwide.

Objective: Quantifying current transfusion practice in intensive care units(ICUs) and investigate differences in transfusion practice between and within different world regions (Europe, America and Asia).

Study design: International multicentre prospective observational point prevalence study. All patients admitted during one week will be included and followed for 28 days. Data regarding general demographic, admission data and transfusion triggers (haemoglobin level, platelet count, PT, APTT, INR, clinical indication) will be collected. For transfused patients and for non-transfused patients the nadir value of transfusion triggers will be collected. Transfusion products (red cell concentrates, plasma, platelets, fibrinogen and co-fact) will be recorded per amount and type.

Study population: Patients admitted to the ICU, 18 years or older.

Main study parameters/endpoints: The number of transfusion products per patient in relation to transfusion triggers. Differences within and between regions will be studied. Secondary outcomes are 28-day mortality and ICU length of stay in relation to transfusion strategy.

Nature and extent of the burden and risks associated with participation, benefit and group relatedness: This study is a descriptive study and only includes objective data collected as part of routine care. No intervention takes place. Therefore, this study does not result in any risk or burdens to patients.

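### Section 5.2 names only tests that assume independent observations, so patient- or event-level comparisons between world regions will give p-values that are too small

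*Protocol*

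**What the plan says.** Protocol section 5.2 fixes the methods for the secondary parameters. For continuous data it states: "Normal data will be analysed using ANOVA analysis or student t-test". It then names Mann-Whitney or Kruskal-Wallis for non-normal data, chi-square or Fisher for categorical data, and a logistic regression of outcome on number of transfusions. The significance level is 0.05. Confidence intervals are promised only for the odds ratios from the logistic regression. Nothing in the protocol mentions clustering, a centre or patient effect, robust variance or an ICU-level analysis.

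The design is clustered at two levels. On sampling, section 2 (Study design) says: "Each centre can choose a week to participate from several pre-specified weeks". All new admissions in that week are then taken. On events, section 3.2 says that "for each transfusion event or administration of coagulations factors a questionnaire will be filled in", so one patient can contribute several records.

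The region comparison appears in the Summary, where the objective is to "investigate differences in transfusion practice between and within different world regions" (Europe, America and Asia), and in section 3.1.2, which lists "Differences of transfusion regimes between world regions" among the secondary parameters. Section 5.1 limits the primary endpoint to descriptive statistics.

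**The concern.** Every ICU lies in exactly one region, so region varies only between ICUs. If patients in the same ICU are transfused more alike than patients in different ICUs, the regional means vary more than an independence-based test allows for. The error then runs in one direction: p-values are too small. The protocol's own rationale expects large heterogeneity in transfusion practice, so an ICC of zero is not a natural working assumption.

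What is at stake is that ordinary ICU-to-ICU variation could be reported as a significant difference between world regions. Repeated events within a patient push event-level comparisons the same way.

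**Working it through.** **Inputs from the protocol.** 10,000 patients, 10-20% of them receiving at least one product, and 1000-2000 transfusion events (section 2.4); three regions (Summary); significance at 0.05 (section 5.2).

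**The plan's own figure.** 10,000 × 0.10 = 1000 and 10,000 × 0.20 = 2000, as stated. This equates patients with at least one product and events, so the event count is a lower bound. No power, effect size or ICC is given, so there is no power figure to reproduce.

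**Assumptions, not in the protocol.** 100 to 500 ICUs of equal size, and ICC 0.01 to 0.10.

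**Formulas.** With m observations per ICU and a factor constant within the ICU, the design effect is DEFF = 1 + (m − 1) × ICC. A three-region test has 2 degrees of freedom and a 5% critical value of 5.99. Its real type I error is P(χ² with 2 df > 5.99/DEFF) = exp(−2.996/DEFF).

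**Outcome measured in all 10,000 patients, such as whether transfused.** For example, with 200 ICUs, m = 50. At ICC 0.05, DEFF = 1 + 49 × 0.05 = 3.45, and exp(−2.996/3.45) = 0.42.

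| ICUs | m | ICC 0.01: DEFF, error | ICC 0.05: DEFF, error | ICC 0.10: DEFF, error |
|---|---|---|---|---|
| 100 | 100 | 1.99, 22% | 5.95, 60% | 10.9, 76% |
| 200 | 50 | 1.49, 13% | 3.45, 42% | 5.90, 60% |
| 300 | 33.3 | 1.32, 10% | 2.62, 32% | 4.23, 49% |
| 500 | 20 | 1.19, 8% | 1.95, 22% | 2.90, 36% |

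**Simulation check.** Beta-binomial data with 15% transfused, three regions and 4000 runs per setting were analysed by a plain chi-square test. With 200 ICUs the rejection rates were 12%, 42% and 60%. An ANOVA of ICU-level rates on the same data gave 3.9% to 5.4% over nine settings (100, 200 or 300 ICUs; ICC 0.01, 0.05 or 0.10).

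**Trigger values among the transfused, 200 ICUs.**

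| Events | m | ICC 0.01: DEFF, error | ICC 0.05: DEFF, error | ICC 0.10: DEFF, error |
|---|---|---|---|---|
| 1000 | 5 | 1.04, 6% | 1.20, 8% | 1.40, 12% |
| 2000 | 10 | 1.09, 6% | 1.45, 13% | 1.90, 21% |

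**Repeats within a patient, taken alone.** Assuming 1.5 to 3 events per transfused patient and a within-patient correlation of 0.3 to 0.7, DEFF runs from 1 + 0.5 × 0.3 = 1.15 to 1 + 2 × 0.7 = 2.40, and the error from 7% to 29%.

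**The case against.** The SAP is not shown, and handling of centre effects is often left to it. Section 5.2 is a short menu that never states the unit of analysis; ANOVA or Kruskal-Wallis on ICU summaries would fit its wording and would be valid. This stands as a limit: the error arises only if the tests are run on patients or events. It does not remove the point. The main endpoint is defined per patient, the forms are per event, and the protocol names independence-based methods without any qualification. A SAP following it at patient or event level would carry the problem forward.

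Several stronger readings are tempting but not supported:

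- *That every test in section 5.2 is equally affected.* The full design effect applies to a factor constant within ICUs. The number of transfusions varies within ICUs, so the standard error in the outcome model need not shrink to the same degree.
- *That reported intervals for regions will be too narrow.* The protocol promises intervals only for the odds ratios of the outcome model.
- *That the effective sample is close to the number of ICUs.* With 200 ICUs and ICC 0.10 it is 10,000/5.90 = 1695, far above 200.
- *That the main result is undermined.* Region is a secondary parameter in section 3.1.2 and is absent from the lists under Objectives. The primary endpoint has no test.
- *That unadjusted region comparisons, or the lack of a named variance measure for differences within regions, are errors of the same kind.* A crude difference is a legitimate description, and descriptive summaries by ICU could show variation within regions. Case-mix adjustment and variance measures are separate analysis choices.

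**Conclusion.** The point holds for p-values in the between-region comparison when the named tests are applied to patients or events. The direction is certain for any positive ICC. The size is not, because the protocol gives neither the number of ICUs nor an ICC.

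For outcomes recorded in all patients, the inflation is serious over most of the assumed range (about 8% to 76% against a nominal 5%) and mild only with many ICUs and a very low ICC. For trigger values among the transfused, it is moderate at 200 ICUs, and within-patient repeats would add to it.

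Because the primary endpoint is descriptive, the study is observational and the remedy needs no new data, this is a should-fix matter.

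**What to change.** Reword section 5.2 so that region comparisons use one of the following:

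- a model with a random intercept for ICU, plus one for patient when the records are transfusion events;
- GEE or cluster-robust standard errors, clustered on ICU;
- an analysis of ICU-level summaries.

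Use ICU-clustered standard errors in the outcome model and after propensity matching as well. It would help to state the expected number of ICUs per region.

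Two additions are optional: a region comparison adjusted for case mix already collected (demographics, SOFA, admission type, shock) beside the crude one, and the between-ICU variance by region as a direct description of differences within regions.

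The cost is a change of text, a little more analysis work, and larger p-values or wider intervals. No new data are needed, provided the ICU identifier is kept in the data set.

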1.2 Relevance

Transfusion practice has already been studied before on the ICU and the operating theater^{17,19–21}. However, these studies were held in a limited number of hospitals within the same country, were limited to only one type of transfusion, are often outdated and difficult generalizable to other hospitals and regions. Since these large observational studies, numerous of randomized controlled trials on RBC transfusion have been published supporting the safety of more restrictive transfusion strategy^{7–10}. However, current

InPUT-study Protocol, dated 09-09-2020

transfusion practice remains unknown. There is a need 1) to describe current transfusion practice for RBC but also for other blood components and coagulation factors, 2) to identify area of improvement, 3) to have large observational data to generate hypotheses on optimal transfusion triggers in subgroups of critically ill patients including patients with brain injury, cardiovascular diseases and elderly patients.

This study will be the first worldwide transfusion practice point prevalence trial on the ICU, which studies the practice of administration of different blood products and coagulation factors.

OBJECTIVES

Primary Objective:

- Number of red blood cell, platelet, and coagulation factors in correlation to haemoglobin levels, platelet count and INR (or PT) respectively.

Secondary Objectives:

- To evaluate which other triggers such as hemodynamic or comorbidities influence RBC transfusion practice.
- To compare haemoglobin levels in transfused patients with nadir levels of haemoglobin in non-transfused patients
- To compare platelet count in transfused patients with platelet to nadir platelet count in non-transfused patients
- To compare INR (or PT) in transfused patients with plasma to nadir level of INR(PT) in non-transfused patients
- To compare transfusion practice between different subgroups of patients including shock septic, haematology, cardiovascular disease without acute coronary diseases and coronary disease
- Association between restrictive and liberal RBC transfusion strategy on ICU length of stay and 28-day mortality
- Association between restrictive and liberal platelet transfusion strategy on ICU length of stay and 28-day mortality
- Association between restrictive and liberal coagulation factor suppletion strategy on ICU length of stay and 28-day mortality

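### Regressing ICU length of stay on the number of transfusions builds in a positive association, because transfusions are recorded over that same stay; for mortality, bias is possible but its direction is uncertain

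*Protocol*

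**What the plan says.** Section 5.2 fixes the model, the exposure and the outcomes: "A logistic regression model will be performed to assess independent association between number of transfusions and outcome", with mortality and ICU length of stay named as the outcomes. It adds: "Results of the logistic regression will be reported as adjusted odds ratio (OR) with 95% confidence intervals". The significance rule is "A p-value <0.05 will be considered to be significant". No exposure window, landmark, per-day rate or time-dependent term is given, and no cut-point for length of stay.

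On when transfusions are recorded, section 3.2 says that "patients will be scored daily using daily questionnaires until discharge with a maximum of 28 days". The daily form holds totals for red cells, platelets and plasma. On outcomes, section 2 says: "Finally after 28 days patient outcome data: length of ICU stay and 28-day mortality will be collected".

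Section 2.4 words the period differently: "in this study we will include all transfusion events during a prespecified week and day".

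The secondary objectives ask about restrictive against liberal strategies for red cells, platelets and coagulation factors, for example "Association between restrictive and liberal coagulation factor suppletion strategy on ICU length of stay and 28-day mortality". Section 5.2 also plans propensity score matching of liberal against restrictive regimes for each product, if enough patients are included.

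**The concern.** A patient can receive an ICU transfusion only while alive and in the ICU. If the count covers the stay, then length of stay is both the outcome and the time available to collect the exposure. Long stayers have higher counts because they stayed longer, whatever transfusion does to them. For mortality, the count depends on how long those who die remain in the ICU compared with those who survive.

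The result is to be reported as an adjusted odds ratio, described as an independent association and tested at 0.05. A reader would take it as evidence about transfusion, when for length of stay part or all of it may simply restate time at risk.

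**Working it through.** **The plan's own figure.** Section 2.4 expects 10-20% of 10 000 patients to receive a product: 10 000 × 0.10 = 1000 and 10 000 × 0.20 = 2000, which reproduces the stated 1000-2000. Strictly these are patients with at least one product, not events. No effect size or power is given for the regression, so there is no further figure to reproduce.

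**Mechanism.** If transfusions occur at rate r per ICU day, the expected count is r × days in the ICU. With r = 0.05 (assumed), a 2-day stay expects 0.05 × 2 = 0.10 transfusions and a 10-day stay 0.05 × 10 = 0.50. The count rises with stay although nothing about transfusion affects stay.

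**Simulation A: no true effect, constant daily transfusion rate.**
- From the protocol: N = 10 000 for the error rates; 10% and 20% ever transfused, and 35% as the middle of the 30-40% cited for red cells over the ICU stay (15% and 35% for the error rates).
- Assumed: mean stay about 3.5-3.7 days, 28-day mortality 28-32%, stay dichotomised at 7 days or at the median, and ICU deaths early, late or at constant hazard.
- Model: logit P(outcome) = a + b × count + c × severity, where severity is the only baseline variable driving stay and death. The true b is 0. Each odds ratio (OR) is from 400 000 patients.

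OR per transfusion:
- Stay above 7 days: 3.1-4.8.
- Stay above the median: 4.2-6.8.
- 28-day mortality, early deaths: 0.58-0.70. Those who died stayed about 2.5 days on average, survivors about 4.1.
- 28-day mortality, late deaths: 1.22-1.30 (about 4.3 against 3.2 days).
- 28-day mortality, constant hazard: 0.91-0.95.

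False-positive rate over 300 replicates of N = 10 000: 100% for stay above 7 days. For mortality it was 98-100% with early or late deaths and 36-60% with constant hazard. Severity was in every model, so baseline adjustment did not remove the bias.

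**Simulation B: no true effect, transfusion rate allowed to fall.** Assumed: daily discharge probability 0.20, daily ICU death risk 0.02, 28-day cap, 19% transfused. OR per transfusion for stay above the median, by how fast the daily transfusion rate falls:
- constant rate: 3.8
- falling 30% per day: 1.9
- falling 50% per day: 1.4
- falling 70% per day: 1.2

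With early deaths instead (risk 0.05 on the first day, falling 20% per day), the mortality OR was about 0.6 at a constant transfusion rate and about 0.8 to 0.96 when the rate fell. This simulation counts ICU deaths only.

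**Other exposure windows** (simulation A, 20% transfused over the stay). Counting only within the study week: stay above 7 days 1.8-2.1, mortality 0.69-1.17. Counting the first 7 ICU days: 2.5-3.0 and 0.66-1.23.

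**After a day-3 landmark** (simulation A). Patients still in the ICU at day 3, transfusions counted up to day 3: OR 1.00-1.02 for mortality and 0.98-1.02 for stay above 7 days. False positives were about 3-7%, consistent with 5% given 300 replicates.

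**Patients lost to a landmark.** The daily chance of remaining is 0.80 × 0.98 = 0.784 with constant death risk, so 0.784² = 0.61 remain after day 2 and 0.784³ = 0.48 after day 3. With early deaths, 0.80² × 0.95 × 0.96 = 0.58 and 0.58 × 0.80 × 0.968 = 0.45. The landmark therefore excludes 39-42% at day 2 and 52-55% at day 3.

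**The case against.** **The window is not stated.** Section 5.2 says only number of transfusions, section 3.2 sets data collection rather than the model's exposure, and section 2.4 speaks of a prespecified week and day. An SAP that is not at hand could define the window. It stands that the whole-stay count is an inference. It does not rescue the model, because exposure and stay still overlap under the study-week reading and the bias remains, though smaller.

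**The size depends on assumptions.** This stands. Transfusions may well cluster early in the stay, which brings the null OR down from about 4 to between 1.2 and 1.9. The direction for length of stay did not change in any scenario.

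**Mortality.** A reader might infer that the model will make transfusion look protective, because early deaths cannot accumulate units. The documents do not support a fixed direction. That depends on whether those who die stay a shorter or longer time than survivors, which the protocol does not say, and under constant risk the bias is close to nil.

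**Match to the objectives.** A reader might also infer that a count of transfusions fails the objectives, which concern strategy. The documents do not support that: the same section plans liberal-against-restrictive propensity matching, conditional on numbers, and the logistic model stands beside it.

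**Importance.** This is a secondary analysis worded as an association, in a study whose primary endpoint is descriptive. This stands and limits the consequences. It does not make the length-of-stay odds ratio interpretable.

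**Conclusion.** The point holds for length of stay. Followed as written, with the count taken over the stay, section 5.2 yields a positive odds ratio when transfusion has no effect. For stay above the median it is about 4 per transfusion with a constant daily rate (4.2-6.8 in simulation A, 3.8 in simulation B) and about 1.2 to 1.9 with a falling rate. These values rest on assumed stays, discharge rates and cut-points; they illustrate the problem and do not predict this study's result. Adjustment for baseline severity does not cure it.

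For mortality the claim is weaker: bias is possible, of uncertain direction and size. Neither a protective nor a harmful artefact can be asserted in advance. The descriptive analysis of the primary endpoint in section 5.1 is not touched.

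**What to change.** In section 5.2, replace the total count by one of the following.

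- **(a) Landmark analysis.** Fix an early ICU day, count transfusions up to it, include only patients still in the ICU on that day, and count death and further stay from then on.
- **(b) Time-dependent exposure.** Use units up to the previous day in discrete-time or cause-specific hazard models for death and for discharge alive. Adjust for baseline variables and for values measured before the units being counted. Do not adjust for haemoglobin, platelet count or INR measured after them, since transfusion changes those values and the adjustment can remove part of the effect being estimated.

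State the exposure window explicitly in either case, and reconcile it with the wording of section 2.4.

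Cost: a change of wording and data preparation, since daily totals for red cells, platelets and plasma are already planned. Option (a) excludes roughly 40-55% of patients at day 2-3 under the assumed discharge rate, so its result applies to longer stayers. Option (b) keeps all patients but needs more modelling. Neither removes confounding by the reason for transfusion; they address only the time problem.
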